#### **Introductory Statement**

The influence of mucosal thickness was shown to be related to marginal bone stability around implants. Several investigators suggested that a minimum of 2 mm peri-implant mucosa thickness was required to prevent peri-implant crestal bone loss on rough surface implants. However, other factors such as implant surfaces may also play a significant role on peri-implant crestal bone level. While previous studies showed the advantages of completely rough implants from machined surface implants (such as faster healing periods and lesser crestal bone loss), its comparable survival rate has been documented. Whether an initial two millimeters mucosal thickness is needed to obtain marginal bone stability around implants with different types of surfaces is still unknown.

## **General Investigational Plan**

A single center, prospective controlled clinical trial is planned to investigate the effect of mucosa tissue thickness upon implant marginal bone changes on implant with smooth collar. Twenty eight adult patients who fulfill the inclusion criteria will be divided into 2 groups based upon the mucosa thickness (<2 mm and ≥2 mm). A signed written informed consent will be obtained from all subjects. Subjects will not be screened or treated until an informed consent has been obtained. Patient information will be protected according to the privacy regulations of the federal Health Insurance Portability and Accountability Act of 1996 (HIPAA).

The enrolled patients will receive implants with polished collar. Implants will be restored at 4 (±1) months after placement. Outcome analyses will be performed until 1 (±1 month) year after loading and clinical and radiographic parameters will be evaluated to compare clinical outcomes between groups. The primary outcome is implant marginal bone loss and probing depth from clinical and radiographic measurements.

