## **Study Protocol**

#### I. Introduction

The thickness of the gingiva (i.e. gingival biotype) varies between subjects. In 1969, Ochsenbein and Ross proposed two main types of gingival biotype ("pronounced scalloped" and "flat") and their relationship with the contour of the osseous crest. Subjects belong to pronounced scalloped biotype have thinner soft buccal tissues and more advanced soft tissue recession than subjects who had the flat biotype. Claffey & Shanley (1986) defined thin tissue biotype as a gingival thickness < 1.5 mm and thick tissue biotype as tissue having thickness ≥ 2 mm.

Several pre-clinical studies have examined how mucosal thickness affects marginal bone loss around implants. Abrahamsson et al. (1996) showed that sites with thin mucosa had an angulated pattern bone defects, whereas sites with an even pattern of the alveolar crest, the adjacent mucosa was consistently thick. Another study by Berglundh and Lindhe (1996) suggested that certain width of the peri-implant mucosa is required to protect osseointegration.

They showed when ridge mucosa was thin ( $\leq 2$  mm), more bone resorption and angular bony defect were noted.

A human prospective clinical trial reported that tissue/mucosa thickness may affect crestal bone stability around implants. Implants with a thick tissue biotype (>2 mm) had significantly less bone loss when compared to implants with thin tissue thickness (≤2 mm). Implants with initially thin tissue had bone loss up to 1.45 mm that occurred within the first year of function. Whereas thick tissues only had 0.2 mm bone loss that was noted. It was observed that thick mucosa formed an epithelial – connective tissue attachment to the titanium surface that protected and preserved the osseointegration. If this soft tissue dimension is not achieved, bone resorption might occur to establish a biological width of the epithelial – connective tissue attachment. Thus, it is suggested that a certain minimum width of peri-implant mucosa is required.

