## **II.** Objectives

The primary objective of this study is to compare the amount of implant marginal bone loss radiographically and probing depth in between thin and thick mucosa group that will receive a machined collar implant.

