## V. Statistical analyses

## Sample size

In this present study, test significance level ( $\alpha$ ) that is used is 5% and the power analysis is 80%. Sample size for each group is calculated using a computer program with two sided equivalence

for difference of proportions in two group design.† According to the previous study mean bone loss of implant placed in thin tissue biotype ( $\mu_1$ ) was 1.450 mm and mean bone loss of implant placed in thick tissue biotype ( $\mu_2$ ) was 0.170 mm. The difference in means in between two groups ( $\mu_1$  -  $\mu_2$ ) was 1.280 mm and common standard deviation was ( $\sigma$ ) was 1.160 mm. Therefore, the sample (n) needed in each group in this present study is 14 patients.

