## **Hypothesis**

Null hypothesis is mucosa thickness does not affect implant marginal bone loss on implant with smooth collar.

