## Statistical analysis

One way ANOVA will be used to detect any differences in between groups and student t test analysis will be conducted to assess mean differences between the groups.

-

†nQuery Advisor®, version 7.0., Los Angeles; Statistical Solutions Inc., 2007

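### Bone loss and probing depth are both named primary, but the hypothesis and sample size cover bone loss only and no deciding visit, testing order or success rule is stated

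*Combined protocol and SAP*

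**What the plan says.** Two places give bone loss and probing depth equal standing. The General Investigational Plan says "The primary outcome is implant marginal bone loss and probing depth from clinical and radiographic measurements". Section II (Objectives) sets the primary objective as being to "compare the amount of implant marginal bone loss radiographically and probing depth in between thin and thick mucosa group".

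The statistical section deals with one outcome only:

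- **Hypothesis:** "Null hypothesis is mucosa thickness does not affect implant marginal bone loss on implant with smooth collar". There is no counterpart for probing depth.
- **Sample size:** the plan says of its significance level "that is used is 5% and the power analysis is 80" (per cent). The inputs are mean bone losses of 1.450 and 0.170 mm, a difference of 1.280 mm and a common SD of 1.160 mm, giving 14 per group. No probing-depth difference or SD appears anywhere.
- **Statistical analysis:** "One way ANOVA will be used to detect any differences in between groups and student t test analysis will be conducted" to compare group means. The sentence names no outcome, visit, order, division of alpha or success rule.

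On timing, the General Investigational Plan says "Outcome analyses will be performed until 1 (±1 month) year after loading". The Outcome analysis table lists marginal bone level at V1, V3, V6, V7, V8 and V9, and probing depth at V4 to V9. No visit is marked as deciding for either outcome.

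**The concern.** With two primary outcomes, the error rate and power of the trial depend on what counts as success: either outcome, both, or one tested before the other. The plan does not choose. As written, a significant probing-depth result with no difference in bone loss could be reported as meeting a primary outcome, although the trial has no hypothesis and no sizing for probing depth. Equally, a significant bone-loss result with no probing-depth difference could be called a failure on the primary objective. The stated 5% and 80% would then not describe the decision actually taken. The rule needs to be fixed before the groups are compared.

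**Working it through.** **Inputs from the documents.** Difference 1.280 mm, SD 1.160 mm, 14 per group, 5% and 80%, two-sided (Sample size). Standardised difference: 1.280/1.160 = 1.10 SD.

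**Inputs not in the documents.** The probing-depth effect (taken as 1.10 SD or 0.8 SD) and the correlation between the two outcomes (taken mainly as 0 to 0.8). These are assumptions, so ranges are shown.

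**Step 1: reproduce the plan's figure.** For a two-sided two-sample t test, the noncentrality is 1.28/(1.16 × √(2/14)) = 2.92, on 26 degrees of freedom, with critical value 2.056.

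- Power at 14 per group: 80.2%.
- Power at 13 per group: 77.0%.

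So 14 is the smallest sufficient number. The normal approximation, 2 × (1.960 + 0.842)² × (1.16/1.28)² = 12.9, gives 13. The plan's 14 is therefore the t-test size for bone loss alone at the full 5%.

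**Step 2: do ANOVA and the t test add a second test?** No. With two groups, F = t², so one-way ANOVA and the equal-variance t test give the same p-value.

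**Step 3: either outcome suffices, each at 5%.** If independent, the family-wise error is 1 − 0.95² = 9.75%. Simulated t tests at 14 per group with no true difference give about 9% at correlation 0.5 and 7.9% at 0.8.

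**Step 4: both outcomes must succeed, each at 5%.** The chance of wrongly claiming success stays at or below 5%. Joint power cannot exceed the bone-loss power of 80.2%.

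| Assumed probing-depth effect | Correlation 0 | 0.5 | 0.8 |
|---|---|---|---|
| 1.10 SD | 64% | 69% | 73% |
| 0.8 SD | 43% | 48% | 52% |

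At correlation 0 the first row is simply 0.802 × 0.802 = 0.64. At an assumed correlation of −0.5, the two rows fall to about 62% and 38%.

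**Step 5: alpha split, 2.5% each.** Family-wise error stays within 5%. Bone-loss power at 14 per group falls to 70.4%, and 17 per group would restore 80%. Power for at least one success is about 80–91% at 1.10 SD and 72–83% at 0.8 SD (correlation 0.8 down to 0). Whether 80% is met therefore depends on inputs the plan does not give.

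**Step 6: bone loss as sole primary, or first in a fixed sequence.** Bone loss is tested at the full 5%, and in the sequence probing depth is tested at 5% only if bone loss is significant. Family-wise error is at most 5% and bone-loss power is 80.2%. No probing-depth assumption is needed.

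**The case against.** **The lead test can be inferred.** The aim, the sole null hypothesis and every sizing input concern bone loss, and follow-up ends about a year after loading. Read that way, 5% and 80.2% both hold and there is no numerical harm. This stands in part: it would be too strong to say that a reader has no idea which result decides the trial. But the inference runs against the explicit primary-outcome sentence and the objective, and no section settles the conflict.

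**The harm is conditional.** A reader might infer that the trial's actual error rate is 9.75%, or its actual power 64–73%. The documents do not support that. They state neither an either rule nor a both rule, and the power figures need probing-depth inputs that the plan lacks. Nor does the plan say that several visits will each be tested for a confirmatory claim. The figures show what each unstated rule would imply.

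**Two primary outcomes can be legitimate.** This stands, provided the rule is stated and the trial is sized for it. Here neither is done.

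**The planning interval.** A reader might infer that the 1.280 mm and 1.160 mm belong to a different period from the one to be analysed. The Introduction describes "bone loss up to 1.45 mm that occurred within the first year of function", whereas V3 to V9 in the Schedule of events is (4±1) months + 3 weeks (0.7 month) + (12±1) months = 14.7 to 18.7 months, or longer. But that sentence says when loss occurred, not from which visit it was measured, and V3 is already labelled baseline. No mismatch is shown; what is missing is a sentence naming the start visit.

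**The sizing label.** The calculation is attributed to "a computer program with two sided equivalence" for proportions. A reader might infer that the sample size is wrong. It is not: 14 reproduces as a comparison of two means. This is a separate wording error and adds no weight to the present point.

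**Conclusion.** The point holds. The plan names two primary outcomes but has a hypothesis and a sample size for one, with no declared deciding visit, testing order or success rule. Bone loss at about 12 months after loading is implied as the lead test but not declared. At 14 per group the documents support 5% and 80% together only with bone loss as sole primary or tested first at the full two-sided 5%. Testing both stated primaries at 5% each does not deliver the two figures together: an either rule can raise the error to about 9.75%, and a both rule leaves the 80% unsupported. The size of the power loss rests on the assumed probing-depth effect and correlation; it is larger with a smaller effect or a negative correlation. The bone-loss figure of 80.2% rests only on the plan's own inputs.

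**What to change.** In the General Investigational Plan, II. Objectives and Statistical analysis, name radiographic marginal bone change to V9 (12 months after crown delivery) as the single primary outcome, compared between groups once by a two-sided 5% t test. Make probing depth at V9 secondary or, to keep it confirmatory, test it at 5% only if bone loss is significant. Results at other visits can be reported descriptively with confidence intervals.

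If the sponsor prefers two equal primaries, the plan should state the either or both rule, give a probing-depth difference and SD, and re-size. As an illustration, requiring both with an equal 1.10 SD effect at correlation 0 needs about 18 per group (bone-loss power 89.5%; 0.895² = 0.80).

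Two side corrections:

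- State that bone change is measured from V3, the labelled baseline, or from another named visit, and say why the planning difference and SD apply to that interval.
- Describe the sample-size calculation as a two-sided comparison of two means.

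The cost is wording. Standardised radiographs at V3, V7 and V9 are already scheduled, and 14 per group stands if bone loss leads. The small downside is that probing depth loses equal primary status. If the planning values cannot be justified for the chosen interval, the sample size would have to be recalculated.

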## **Study Protocol**

#### I. Introduction

The thickness of the gingiva (i.e. gingival biotype) varies between subjects. In 1969, Ochsenbein and Ross proposed two main types of gingival biotype ("pronounced scalloped" and "flat") and their relationship with the contour of the osseous crest. Subjects belong to pronounced scalloped biotype have thinner soft buccal tissues and more advanced soft tissue recession than subjects who had the flat biotype. Claffey & Shanley (1986) defined thin tissue biotype as a gingival thickness < 1.5 mm and thick tissue biotype as tissue having thickness ≥ 2 mm.

Several pre-clinical studies have examined how mucosal thickness affects marginal bone loss around implants. Abrahamsson et al. (1996) showed that sites with thin mucosa had an angulated pattern bone defects, whereas sites with an even pattern of the alveolar crest, the adjacent mucosa was consistently thick. Another study by Berglundh and Lindhe (1996) suggested that certain width of the peri-implant mucosa is required to protect osseointegration.

They showed when ridge mucosa was thin ( $\leq 2$  mm), more bone resorption and angular bony defect were noted.

A human prospective clinical trial reported that tissue/mucosa thickness may affect crestal bone stability around implants. Implants with a thick tissue biotype (>2 mm) had significantly less bone loss when compared to implants with thin tissue thickness (≤2 mm). Implants with initially thin tissue had bone loss up to 1.45 mm that occurred within the first year of function. Whereas thick tissues only had 0.2 mm bone loss that was noted. It was observed that thick mucosa formed an epithelial – connective tissue attachment to the titanium surface that protected and preserved the osseointegration. If this soft tissue dimension is not achieved, bone resorption might occur to establish a biological width of the epithelial – connective tissue attachment. Thus, it is suggested that a certain minimum width of peri-implant mucosa is required.

Recently, researches have shown implant surfaces may play a critical role for long-term implant success. Bacteria pathogens have been proposed as the main etiology factor of peri-implantitis leading to implant failure. Therefore, implant design that can help reduce plaque retention is important to facilitate good oral hygiene. Originally, smooth/polished collar implants were developed because it is easier to clean and harbors less plaque than rough surface implant. Concurrently, this has been changed to predominantly rough-coated surface to enhance osseointegration as well as a shortened waiting time. However, a study that compared the implant survival rate of smooth- and rough-surfaced implants showed similar survival rate (94%).

To date, the influence of mucosa tissue thickness upon implant crestal bone loss on implant with smooth surface collar has not been determined yet. Hence, the aim of this study is to test the effect of mucosa tissue thickness upon implant marginal bone changes on implant with smooth collars.

## **II.** Objectives

The primary objective of this study is to compare the amount of implant marginal bone loss radiographically and probing depth in between thin and thick mucosa group that will receive a machined collar implant.

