#### **B.** Clinical assessments

Clinical measurements (probing depth, clinical attachment level and bleeding on probing) will be recorded using a UNC (University of North Carolina) manual probe. These measurements will be taken at two weeks post-operatory (V4), one month post-operatory (V5), crown impression (V6), crown restoration (V7), 6 months (V8), and 12 months (V9) after crown restoration. A tension-free caliper will be used to measure mucosa thickness at the time of surgery. Clinical photographs will be taken at each appointment as well as standardized radiographs. In addition, bone sounding procedure under local anesthesia will be performed on the mid buccal and lingual side of the implant sites at 12 month follow-up to assess the level of the underlying bone. Subjects will also be receiving a cleaning at no charge to them at their 6 and 12 month visits.

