## D. Surgical protocol

Preliminary alginate impressions will be taken at the screening appointment for the purpose of making study models to then be able to fabricate a reference stent and surgical guide. On the

implant surgery visitvital signs will be taken. Local anesthesia will be performed by using local infiltration technique with 2% Lidocaine with 1:100k epinephrine or 1:50k epinephrine. Intrasulcular and crestal incision design will be made along the crest of the ridge, bisecting the existing zone of keratinized mucosa. Full-thickness flaps are raised on the buccal and lingual/palatal side up to or slightly beyond the level of the mucogingival junction, exposing the alveolar ridge of the implant surgical sites. Once the flaps are reflected and the bone is prepared, a surgical guide will be inserted and a series of drills are used to prepare the osteotomy site incrementally. All implants will be placed according to the manufacturer's protocol (Biohorizons Tapered Internal Implant, Laser-Lok, RBT) and the rough-smooth junction will be placed to the bone crest. The buccal mucosal thickness will be measured at different levels. Implants with 9-13 mm length and 3-5 mm width will be used. After implant placement a healing abutment will be connected and interrupted sutures will be placed to close the flaps. After suturing, standardized radiographs will be obtained. Other radiographs will be taken during the surgery to check implant angulation, these will not be standardized. The surgery is being done as part of standard of care. Subjects will be instructed to rinse with warm salt water once a day every day for two weeks. All subjects will be prescribed 500mg of amoxicillin to take 3 times a day for ten days. If the subject is allergic to Amoxicillin, they will be prescribed 250 mg of Zithromax 6 tablets total /sig. 2 tablets the 1st day and Q.D. (1 x per day) until gone. In addition, the subject will be prescribed 600 mg of ibuprofen, taken as needed, for pain control. The sutures will be removed in 2 weeks.

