# IV. Outcome analysis

The measurement variables and correspondent measurement time points are summarized in the Table.

Measurement time	Measurements						
Clinical outcomes							
Baseline (V3)	Mucosa thickness						
At two weeks post-operatory (V4), one month post-operatory (V5), crown impression (V6), and at crown delivery (V7),	Probing depth, bleeding on probing, clinical attachment level						
6 (V8) and 12m (V9) after crown placement	Probing depth, bleeding on probing, clinical attachment level						
Radiographic outcome							
	Marginal bone level						
At screening (V1), implant/surgery baseline (V3), crown impression (V6), crown delivery (V7), 6m (V8), and 12m (V9) after crown placement.							

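### Probing depth shares primary status with bone loss without its own hypothesis, sample size or defined analysis, and it may partly reflect the mucosa thickness that forms the groups

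*Combined protocol and SAP*

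**What the plan says.** - **Primary outcome.** The General Investigational Plan states: "The primary outcome is implant marginal bone loss and probing depth from clinical and radiographic measurements". Section II (Objectives) repeats the pairing, comparing radiographic bone loss and "probing depth in between thin and thick mucosa group that will receive a machined collar implant". Neither place ranks the two.
- **Groups.** Patients are not randomised. They "will be divided into 2 groups based upon the mucosa thickness", with the cut at 2 mm.
- **Hypothesis and aim.** The null hypothesis is that "mucosa thickness does not affect implant marginal bone loss on implant with smooth collar". The aim at the end of the Introduction also concerns marginal bone only. Neither mentions probing depth.
- **Sample size.** The inputs are bone-loss means and an SD. None relates to probing depth.
- **Analysis.** The plan is a one-way ANOVA, and "student t test analysis will be conducted to assess mean differences between the groups". No visit, reference value, change score or covariate is named.
- **Timing.** Section IV schedules probing depth at V4 to V7 and again at "6 (V8) and 12m (V9) after crown placement". There is no pre-implant probing depth.
- **Geometry.** Under III.D, "the rough-smooth junction will be placed to the bone crest". The same section describes the thickness measurement as buccal, at several levels. III.B adds that a caliper is used at surgery. Neither says whether the thickness is vertical or horizontal.

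**The concern.** Probing depth is read within the soft tissue around the implant, and the thickness of that tissue defines the groups. With the rough-smooth junction set at the crest, a thick site may probe deeper from the start without any bone change. In the other direction, bone loss at a thin site would deepen probing while thin tissue would make it shallower, so the two could offset. The Introduction's own rationale points the same way: bone may resorb until the needed soft-tissue width is established, so a thin site could lose bone and end with a soft-tissue dimension like that of a thick site.

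The only hypothesis against which a probing-depth result can be read is about bone loss. Read that way, a significant difference need not mean bone change and a null result need not mean stability. Because depth is recorded at six visits and none is chosen, the visit and the form of the comparison can also be settled after the data are seen. Finally, two unranked primary outcomes give two chances of a positive finding.

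**Working it through.** **1. The plan's own figure.** Inputs from the Sample size section: difference 1.280 mm, SD 1.160 mm, two-sided 5%, power 80%. Standardised difference = 1.280/1.160 = 1.103.
- Normal approximation: n = 2(1.960 + 0.842)²/1.103² = 12.9, so 13 per group.
- Two-sample t test (noncentral t): 13.92, so 14 per group, with power 80.2% at 14.

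The stated 14 is reproduced, and every input is a bone-loss quantity. It says nothing about power for probing depth.

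**2. Carry-over of thickness into depth.** The documents give no probing-depth SD, thickness distribution or slope of depth on thickness, so these are assumptions: within-group SD 0.8-1.0 mm, and a shift c in mean V9 depth due to thickness alone. With 14 per group and no change after loading, the noncentrality is c / (SD × √(2/14)), with √(2/14) = 0.378, and the critical t on 26 df is 2.056.

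| c (mm) | Noncentrality, SD 1.0 | Significant, SD 1.0 | Noncentrality, SD 0.8 | Significant, SD 0.8 |
|---|---|---|---|---|
| 0 | 0 | 5% | 0 | 5% |
| 0.25 | 0.66 | 9.8% | 0.83 | 12.5% |
| 0.5 | 1.32 | 24.7% | 1.65 | 35.7% |
| 1.0 | 2.65 | 72.1% | 3.31 | 88.9% |

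**3. Masking.** Suppose, again as an assumption, that the planned 1.28 mm bone difference passed fully into probing depth, with SD 1.0 mm. The net difference is 1.28 − c.
- c = 0: net 1.28 mm, power 90%.
- c = 0.5: net 0.78 mm, power 51%.
- c = 1.0: net 0.28 mm, power 11%.

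**4. Two primary outcomes.** If either can carry the claim, each is tested at 5% and they are independent, the family-wise error is 1 − 0.95² = 9.75%. Splitting alpha to 2.5% each would need 17 per group on the bone-loss inputs (16.93 rounded up). Power at 14 would be 70.4%.

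**5. Which probing-depth analysis removes a constant offset.** Assume the same shift c at V7 and V9, equal SDs and V7-V9 correlation r, with no change after loading.
- Simple change V9 − V7: expected group difference c − c = 0. Simulated rejection is about 5%.
- ANCOVA on V7 depth: the within-group slope is r, so the expected group effect is c − r·c = c(1 − r). For r = 0.5-0.7 this is 0.15-0.25 mm at c = 0.5 and 0.30-0.50 mm at c = 1.0. Simulated with 14 per group and SD 0.8-1.0 mm, it rejects about 8-14% and 15-34% of the time. Using change as the response with V7 as a covariate gives the same group coefficient, so it does not help.
- Precision of simple change: variance = 2(1 − r)SD², which is 1.0 × SD² at r = 0.5 and 0.6 × SD² at r = 0.7. It is noisier than a single V9 value only if r is below 0.5.

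**The case against.** The strongest reply has four parts.

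- **The plan never says that unadjusted 12-month depths will be compared.** A reader might infer that it commits to this. It does not: the wording fits a value or a change, at any visit. What stands is that the endpoint is undefined and a V9 comparison is allowed.
- **Deeper probing in the thick group does not follow by definition.** That reading needs a vertical (crestal) thickness. The protocol speaks of buccal thickness at different levels. If that is horizontal, the link to depth is weaker. This objection stands, and the coupling is plausible but not established.
- **The sizes rest on assumptions.** This also stands. With no carry-over there is no distortion, and at 0.25 mm it is modest (10-13%). The Introduction's biological-width argument could itself imply that soft-tissue dimensions converge.
- **Probing depth is a legitimate outcome in its own right.** If so, a difference between thickness groups is an answer, not an artefact. That is fair, but the plan states no hypothesis or intended interpretation for probing depth, and the only hypothesis present is about bone.

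As to multiplicity, 9.75% assumes that a positive result on either outcome suffices. If both were required there would be no inflation. The plan does not say which applies.

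**Conclusion.** The point holds as one of outcome hierarchy and an undefined endpoint. Probing depth has primary status without a hypothesis, sample size, visit or form of analysis, in groups formed by a variable on which it may partly depend. Under the stated assumptions (14 per group, SD 0.8-1.0 mm), the chance of a significant V9 difference with no change after loading runs from 5% with no carry-over to 72-89% at 1.0 mm. The documents cannot place the trial within that range.

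A reader might go further and infer that the bone-loss conclusion is compromised. The documents do not support that: marginal bone level is assessed on radiographs separately from probing, and the bone-loss hypothesis and sample size stand apart from probing depth. The distortion arises when probing depth is read as evidence about bone. The change should be made, but it does not threaten the trial's main result.

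**What to change.** 1. In the General Investigational Plan and section II, name radiographic marginal bone loss as the single primary outcome and make probing depth secondary. This matches the existing hypothesis and sample size and removes the two-outcome multiplicity.
2. In the Statistical analysis section, define the probing-depth analysis as each patient's V9 depth minus V7 depth, compared between groups by t test. Report depths at every visit descriptively by group.
3. Do not make ANCOVA on V7 depth the main analysis. In non-randomised groups that may differ at V7 it leaves a residual bias of c(1 − r).
4. State whether the thickness that defines the groups is vertical or horizontal, so that readers can judge the coupling.

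The cost is wording only, since V7 and V9 probing are already scheduled. There are two downsides. Probing depth loses primary status. Change before V7 is only described, which matters because a healing abutment is connected at placement and tissue adaptation may begin before crown delivery.
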